### **4.2     Scientific Rationale for Study Design**

As stated in ICH guideline E4, “Knowledge of the relationships among dose, drug concentration drug concentration in blood, and clinical response (effectiveness and undesirable effects) is important for the safe and effective use of drugs in individual patients. This information can help identify an appropriate starting dose, the best way to adjust dosage to the needs of a particular patient, and a dose beyond which increases would be unlikely to provide added benefit or would produce unacceptable side effects.”

### **4.3     Justification for Dose**

The dose used for this study will be the dose approved by FDA as described in the prescribing information for CYTALUX™ (pafolacianine) injection.

### **4.4     End of Study Definition**

A participant is considered to have completed the study if they have completed all phases of the study including the last visit or the last scheduled procedure shown in the Schedule of Activities (SoA), Section 1.3.

The end of the study is defined as completion of the last visit or procedure shown in the SoA.

## **5     STUDY POPULATION**

Adult subjects (>18 years old) who are presumed high-risk patients or have advanced disease, and/or recurrent disease. Pregnant patients will be excluded.

### **5.1     Inclusion Criteria**

In order to be eligible to participate in this study, an individual must meet all of the following criteria:

1. Provision of signed and dated informed consent form
2. Adult subjects 18 years of age and older
3. Primary diagnosis of endometrial cancer
4. Scheduled to undergo surgery for endometrial cancer
5. Ability to understand the requirements of the study and agree to abide by the study restrictions and to return for the required assessments

03 Sep 2025

6. Willingness to stop the use of folate or folic acid supplements at least 48 hours prior to infusion of study drug

## 5.2 Exclusion Criteria

An individual who meets any of the following criteria will be excluded from participation in this study:

1. Pregnancy or positive pregnancy test
2. Any medical condition that in the opinion of the investigator could potentially jeopardize the safety of the subject
3. History of anaphylactic reactions to products containing indocyanine green
4. History of allergy to any of the components of CYTALUX
5. Presence of any psychological, familial, sociological condition or geographical challenges potentially hampering compliance with the study protocol or follow-up schedule

## 5.3 Lifestyle Considerations

None.

## 5.4 Screen Failures

Screen failures are defined as participants who consent to participate in the clinical trial but are not subsequently entered in the study. A minimal set of screen failure information is required to ensure transparent reporting of screen failure participants, to meet the Consolidated Standards of Reporting Trials (CONSORT) publishing requirements and to respond to queries from regulatory authorities. Minimal information includes demography, screen failure details, eligibility criteria, and any serious adverse event (SAE).

## 5.5 Strategies for Recruitment and Retention

Subjects will be recruited from the clinical practice of each Investigator. Follow-up visits are set to correspond with normal post-operative follow-ups by the surgeon. Retention is not expected to be a problem.

# 6 STUDY INTERVENTION

## 6.1 Study Intervention(s) Administration

### 6.1.1 *Study Intervention Description*

CYTALUX will be supplied in vials containing 1.6 mL of solution of 2 mg/mL OTL38 for a total of 3.2 mg of drug per vial. The contents of the vial are a frozen blue-green solution.

03 Sep 2025

### 6.1.2 Dosing and Administration

The planned dose 0.025 mg/KG will be administered via IV over 60 minutes. Subjects will complete a single intravenous dose not less than 1 hour before and not more than 168 hours (7 days) before initiation of intraoperative fluorescent imaging. Pre-treatment with antihistamines and/or anti-nausea medication may be used. If the patient develops any symptoms or signs suggestive of a hypersensitivity reaction, including during infusion of the study drug, an antihistamine, and/or antiemetic may be administered based on the clinical judgement of the investigator. If such symptoms or signs suggestive of hypersensitivity develop during the infusion of the study drug, the infusion may be interrupted and then resumed based on the clinical judgement of the Investigator on the condition of the patient.

Folic acid may reduce the detection of cancerous tissue with CYTALUX. Patients should stop taking folate, folic acid, or folate-containing supplements 48 hours before administration of CYTALUX.

[figure not shown]
Note that CYTALUX should not be mixed with other medicinal products and should not be given simultaneously through the same IV line as another medicine.

### 6.1.3 Camera/Imaging System

The following are specifications for the imaging systems to be used in this study.

**Spectral specifications:** The light engine will provide an excitation channel that closely matches the optimal excitation wavelength of OTL38. As shown in [Figure 1](#), OTL38 responds to light between the wavelengths of 760-776 nm with maximum excitation at 774-776 nm, and fluoresces, i.e., emits light at wavelengths in the near-infrared (NIR) spectrum (maximum emission 794-796 nm).

**Figure 1. Excitation and Emission Spectra of OTL38**

Exact spectral data for OTL38 is obtained using 1  $\mu$ M of OTL38 in phosphate buffered saline with Cay Eclipse Fluorescence Spectrophotometer (Agilent) with auto filter setting in the Research and Development facility, On Target Laboratories, West Lafayette, IN.

03 Sep 2025

**Temperature:** The temperature (T) of the camera head will not exceed 42°C. The limit  $T \leq 42^\circ\text{C}$  is taken from IEC60601-2-18 (Medical electrical equipment: Particular requirements for the basic safety and essential performance of endoscopic equipment).

**Electrical and Electromagnetic Compatibility (EMC):** The light engine will conform to international standards for EMC emission and susceptibility, as well as other specifications in IEC 60601-1-2.

**Operating Conditions:** The system shall function normally over the following range of environmental conditions:

Temperature:  $+10^\circ\text{ C}$  to  $+30^\circ\text{ C}$ , at sea level

Relative humidity: 10% to 85%, non-condensing

**Enclosure:** Rough surfaces, sharp corners and edges that could result in an unacceptable risk shall be avoided or covered.

Enclosure of the video processor / illuminator shall prevent fingers from reaching hazardous internal components.

**Sterilization:** Any component requiring sterilization shall tolerate the appropriate method of sterilization.

**Draping:** Drapes shall be provided to make the system suitable for application in the sterile field.

**Light Power – Maximum Power at Exit of Illuminator:** The maximum light power at the exit of the illuminator shall comply with skin and tissue exposure limits as defined by IEC 60825-1 and CIE S009.

**Standard – Class 3R Laser Product:** The system shall comply with the safety requirements for a Class 3R laser product according to IEC 60825-1:2007.

**Standard – Radiation Safety:** The system shall comply with the standard or broadband radiation CIE S009/E:2002.

**Standard – General Safety:** The system shall comply with general safety standards IEC 60601-1:2005 and IEC 60601-2-18, including all applicable amendments.

**Training and Intended Use:** The system can only be used by clinicians that have been qualified as trained by the system provider or the sponsor, and only for the intended use in this clinical study protocol that has been approved by an IRB.

## **6.2 Preparation/ Handling/ Storage/ Accountability**

### **6.2.1 Acquisition and Accountability**

CYTALUX will be provided by On Target Laboratories. The vials must be stored in a secure, temperature-controlled freezer with limited access. Unused, partially used and/or empty vials will be disposed of on-site according to standard site procedures.

03 Sep 2025

A Pharmacist or other trained and qualified healthcare professional will prepare the IV solutions according to the manufacturer's label.

#### **6.2.2 *Formulation, Appearance, Packaging and Labeling***

The study medication will be packaged in vials and labelled by On Target Laboratories' clinical supplies designee.

Study medication should be stored in a freezer at temperature -20°C, and with protection from light.

A Pharmacist or other trained and qualified healthcare professional will prepare the IV solutions according to the manufacturer's label. All prepared solutions should be protected from light and refrigerated (between 2-8°C) until use.

#### **6.2.3 *Product Storage and Stability***

Study medication should be stored in a freezer at temperature, -25 to -15°C, and with protection from light. If not immediately used, store the diluted CYTALUX infusion solution in a refrigerator at 2°C to 8°C for not more than 24 hours. Once the bag is removed from refrigeration, the infusion must be completed within 3 hours.

#### **6.2.4 *Preparation***

CYTALUX will be prepared according to the manufacturer's prescribing information.

Note that CYTALUX should not be mixed with other medicinal products and should not be given simultaneously through the same IV line as another medicine.

### **6.3 Measures to Minimize Bias – Randomization and Blinding**

This trial will be an open-label study with no randomization or blinding. All subjects will receive the study drug.

#### **6.4 Study Intervention Compliance**

The IV infusion will be performed by qualified personnel and overseen by the investigator or a medically qualified delegate. The date and time of the infusion will be recorded, as well as the amount infused. Subjects may elect to have the infusion discontinued as for example if they withdraw consent for the study, or experience one or more adverse events that are suspected to be attributable to the test article or its infusion.

#### **6.5 Concomitant Therapy**

Necessary supportive measures for optimal medical care will be given throughout the study. Additional care may be administered as indicated at the discretion of the treating physician, and where appropriate after discussion with the medical monitor. Concomitant medications will include all medications that started, or were continuing, during or after administration of the study drug.

The following concomitant medications are prohibited within 48 hours prior to drug administration: folic acid, folate supplements, and multi-vitamins containing folate.

03 Sep 2025

## 6.6 Rescue Medication

Rescue medication is not applicable to this study.

# 7 STUDY INTERVENTION DISCONTINUATION AND PARTICIPANT DISCONTINUATION/WITHDRAWAL

## 7.1 Discontinuation of Study Intervention

Discontinuation from infusion of CYTALUX does not mean discontinuation from the study, and remaining study procedures should be completed as indicated by the study protocol. If a clinically significant finding is identified (including, but not limited to, changes from baseline) after enrollment, the investigator or qualified designee will determine if any change in participant management is needed. Any new clinically relevant finding will be reported as an adverse event (AE).

The data to be collected at the time of study intervention discontinuation will include the following:

- The weight of the infusion bag, or a measurement of remaining volume
- The time of discontinuation
- The reason for discontinuation

## 7.2 Participant Discontinuation / Withdrawal from the Study

Subjects are free to withdraw from participation in the study at any time upon request.

An investigator may discontinue or withdraw a participant from the study for the following reasons:

- If any clinical adverse event (AE), laboratory abnormality, or other medical condition or situation occurs such that continued participation in the study would not be in the best interest of the participant
- Cancelation or rescheduling surgery
- If the participant meets an exclusion criterion (either newly developed or not previously recognized) that precludes further study participation

The reason for discontinuation or withdrawal from the study will be recorded. Subjects who sign the informed consent form and are randomized but do not receive the study intervention may be replaced. Subjects who sign the informed consent form, and are randomized and receive the study intervention, and subsequently withdraw, or are withdrawn or discontinued from the study, will not be replaced.

## 7.3 Lost to Follow-up

A subject will be considered lost to follow-up if they fail to return for scheduled safety follow-up visits and is unable to be contacted by the study site staff.

The following actions must be taken if a participant fails to return to the clinic for a required study visit:

- The site will attempt to contact the participant and reschedule the missed visit within one week of the target date, and counsel the participant on the importance of maintaining the assigned visit schedule and ascertain if the participant wishes to and/or should continue in the study.
- Before a participant is deemed lost to follow-up, the investigator or designee will make every effort to regain contact with the participant (where possible, 3 telephone calls and, if necessary, a certified letter to the participant's last known mailing address or local equivalent methods). These contact attempts should be documented in the participant's medical record or study file.

Should the participant continue to be unreachable, he or she will be considered to have withdrawn from the study with a primary reason of lost to follow-up.

03 Sep 2025

## 8 STUDY ASSESSMENTS AND PROCEDURES

### 8.1 Study Activities by Visit

Each subject who enters study screening (i.e. signs an informed consent form) will be assigned a subject ID number for traceability. Any subject who signs an informed consent but fails to meet the eligibility criteria is considered to be a Screen Failure. Screen Failure subjects will have their demographic information and reason for screen failure captured.

#### 8.1.1 Screening Visit

*[Purpose: To determine initial eligibility and assign dose timing]*

Screening can take place up to 30 days prior to the scheduled surgery. Prior to the initiation of study-specific screening assessments the Investigator or designee must provide the patient with a complete explanation of the purpose of the study and the planned evaluations (procedures and assessments). To be screened, the patient must sign and receive a copy of an Informed Consent Form and authorization of use and disclosure of protected health information (PHI) that was approved by the governing IRB. All consenting subjects will be screened for trial eligibility by completing the following procedures at this visit:

1. Assess all Inclusion/Exclusion Criteria
2. Obtain demographic data
3. Record endometrial cancer diagnosis information
4. Record relevant medical history

#### 8.1.2 Visit 1: Infusion

*[Purpose: To infuse CYTALUX™ (PAFOLACIANINE) INJECTION]*

1. Patients with a known allergy to CYTALUX (pafolacianine) will be given pre-medication of 25 mg Benadryl and 4 mg Zofran as prophylaxis approximately 30 minutes prior to the start of infusion, unless a patient has a history of allergy to either drug.
2. A single dose of CYTALUX will be infused IV over 60 minutes
3. AEs will be recorded during infusion of CYTALUX.

Should the patient experience suspected adverse events during infusion, the infusion will be stopped, and the Principal Investigator (PI) will be contacted for discussion and assessment. Per PI discretion, the patient will be treated for symptoms and infusion can be started again to assess for tolerance. If infusion is still not tolerated, amount infused will be recorded and imaging portion of study will proceed.

4. Intraoperative imaging should begin within 1 to 168 hours (7 days) after the completion of infusion.

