#### 4.1.1 Screening

Screening will overlap with the routine/standard pre-operative screening conducted by the hospital where the surgery is scheduled. Consented patients will be evaluated for eligibility prior to any non-screening study related procedures being performed.

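### Visit 1 premedicates patients with a known CYTALUX allergy ahead of the infusion, although exclusion criterion 4 bars those patients from the study

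*Protocol*

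**What the plan says.** Four parts of the protocol bear on this.

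- **Eligibility (section 5.2).** The list of exclusions opens with "An individual who meets any of the following criteria will be excluded from participation in this study". Criterion 4 reads "History of allergy to any of the components of CYTALUX".
- **Screening (sections 4.1.1 and 8.1.1).** The screening visit includes the step "Assess all Inclusion/Exclusion Criteria", and section 4.1.1 fixes the order: "Consented patients will be evaluated for eligibility prior to any non-screening study related procedures being performed". Under section 8.1, a consented subject who does not meet the criteria is a screen failure.
- **Infusion visit (section 8.1.2).** Step 1: "Patients with a known allergy to CYTALUX (pafolacianine) will be given pre-medication of 25 mg Benadryl and 4 mg Zofran as prophylaxis". This is to happen roughly 30 minutes before the infusion starts, and the only carve-out is for allergy to either premedication drug. Step 2: "A single dose of CYTALUX will be infused IV over 60 minutes".
- **Dosing (section 6.1.2).** Premedication appears here as a general option: "Pre-treatment with antihistamines and/or anti-nausea medication may be used". No patient group is named.

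Section 7.2 deals with exclusion criteria that emerge or are noticed late. It lists them among reasons introduced by "An investigator may discontinue or withdraw a participant from the study for the following reasons".

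**The concern.** The eligibility section removes patients with a CYTALUX allergy from the trial, while the dosing-visit section tells staff how to prepare such patients for the infusion. Both use mandatory language, and they point in opposite directions on a safety matter.

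The conflict would bite when an allergy is overlooked at screening or comes to light afterwards. Screening may take place up to 30 days before surgery, and the schedule in section 1.3 lists only a pregnancy test, drug administration and adverse event assessment at Visit 1, with no allergy re-check. At the point of dosing, the visit instructions mention a known CYTALUX allergy only to call for premedication before infusion.

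There is a second possibility: that step 1 was meant for some other group. In that case its mandatory premedication reaches none of the intended patients as written, and they fall back on the optional wording of section 6.1.2.

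**Working it through.** No formula or rate applies. The check sets the passages side by side and tests whether any reading lets them coexist.

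**1. Are the two groups the same?** Criterion 4 covers allergy to any component of CYTALUX. Step 1 covers known allergy to CYTALUX, with pafolacianine named in brackets. Section 2.1 gives CYTALUX as the trade name of pafolacianine, so pafolacianine is a component. The step 1 group therefore lies wholly within the criterion 4 group.

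**2. Does step 1 lead to infusion?** Step 2 does not name allergic patients, so this is an inference. It is a firm one: the premedication is timed relative to the start of the infusion, and step 2 makes no exception.

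**3. Could step 1 refer to another allergy?** No. The reference to allergy to either drug concerns Benadryl and Zofran and only limits who receives them. The trigger is allergy to CYTALUX by name.

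**4. Could step 1 mean a reaction arising during the study?** No. The study gives a single dose, step 1 speaks of an allergy already known before that dose, and reactions during infusion are handled separately later in section 8.1.2 and in section 6.1.2.

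**5. Does section 7.2 settle the matter?** No. It permits the investigator to withdraw a participant whose exclusion criterion is recognised late. It does not require withdrawal, does not provide for premedicating and infusing, and leaves step 1 standing.

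**6. What follows under each reading?**

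| Situation | Section 5.2 | Section 8.1.2 steps 1 and 2 |
|---|---|---|
| Allergy known at screening, criterion 4 applied | Patient excluded | Step 1 applies to 0 of 10 planned subjects |
| Allergy missed or recognised after screening | Patient meets an exclusion criterion | Patient premedicated, then infused |

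The 0 of 10 follows from the definitions and is not an estimate. Section 2.4.1 reports hypersensitivity in 2% of 406 treated patients, but that describes reactions on treatment. It is not a rate of known allergy before treatment, and the protocol gives no such rate.

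**7. Premedication wording.** Section 6.1.2 makes it optional for anyone. Section 2.4.1 describes it as frequent practice to limit side effects, without tying it to allergy. Section 8.1.2 makes it mandatory, but only for a group the protocol excludes. The intended rule cannot be recovered from these three places.

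**The case against.** The best case for leaving this alone is that its practical reach is small. Exclusion is mandatory, all criteria are checked before any non-screening procedure, and a failing subject never reaches Visit 1. In the ordinary course step 1 is inoperative rather than dangerous.

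Nor do the exclusion criteria lapse after screening. Section 8.1.1 describes screening as determining initial eligibility, the Visit 1 pregnancy test shows that eligibility is still being applied then, and section 7.2 expressly contemplates late-recognised criteria. Section 6.4 has the infusion overseen by the investigator or a medically qualified delegate. Staff would therefore have more than step 1 to go on.

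On premedication, a general permission and a specific requirement for one subgroup can coexist, and section 6.1.2 still allows premedication for any enrolled patient.

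Much of this stands. Harm is conditional on a screening miss or late recognition, its frequency is unknown, and no endpoint or analysis is touched. The premedication point is secondary, because its main defect is that the named subgroup is excluded. None of it removes the contradiction: the other safeguards point toward exclusion or withdrawal, which is exactly what step 1 does not do.

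**Conclusion.** The contradiction is real and should be corrected before enrolment. As written, step 1 of Visit 1 either applies to no eligible patient or directs preparation for infusion of a patient whom section 5.2 excludes.

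This rests on two readings, both well supported by the text: that pafolacianine counts as a component of CYTALUX, and that premedication timed to the start of the infusion implies the infusion follows. The number of patients who could be affected cannot be stated. The case for correction rests on the operative dosing instructions contradicting the eligibility criteria on a safety point, and not on any effect on the statistical results.

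**What to change.** - Reconcile sections 5.2, 7.2 and 8.1.2 so that one consistent statement covers patients with known CYTALUX allergy, including an allergy first recognised after screening.
- Reconcile sections 6.1.2 and 8.1.2 on which patients the premedication is for and whether it is optional or mandatory.
- As a minor point for the same edit, align the wording on halting the infusion. Section 6.1.2 leaves interruption for signs of hypersensitivity to the investigator's judgement, whereas section 8.1.2 says the infusion is stopped for suspected adverse events and the principal investigator contacted.

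Which clinical rule stands in each case is for the sponsor's clinicians. The cost is a protocol wording change before enrolment, with no effect on sample size or analysis.
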